8.3.5 Demographic and Baseline Characteristics

Demographic and Baseline characteristics will be summarized by treatment group for the Safety and mITT populations (and for the PP population, if a PP analysis is performed) using descriptive statistics.

Categorical variables (such as sex, race, ethnicity) will be summarized by the number and percentage of subjects with each relevant characteristic in each treatment group. Continuous variables such as (age) will be summarized by mean, SD, median, minimum and maximum values in each treatment group.

8.3.6 Study Product Compliance and Use of Other Therapies

8.3.6.1 Prior and Concomitant Medications

Prior medications/non-drug therapies and concomitant medications/significant non-drug therapies taken during the study will be listed for the Safety population.

8.3.7 Handling of Dropouts and Missing Data

MMRM analyses account for missing data using ‘a missing at random’ assumption, i.e., there is a systematic relationship between the propensity for missing values and the observed data, but not the missing data.

Under such assumptions, MMRM is shown to provide unbiased estimates of the treatment effect whilst analysis of only complete cases using analysis of covariance (ANCOVA) is biased (Ashbeck, 2016; Baron, 2008).

Such complete case analysis requires a ‘missing completely at random’ assumption to remain unbiased and this is unlikely to hold, i.e., the fact that the data are missing is independent of the observed and unobserved data.

Using an MMRM, it will therefore be assumed that a subject with missing data at one post-Baseline assessment visit would have obtained a similar efficacy result at that visit compared to a subject using the same investigational product with similar non-missing results at other timepoints (Baseline and the other post-Baseline assessment visits).

9 APPENDICES

9.1 Adverse Event (AE) and Serious AE (SAE)

The investigator and any qualified designees are responsible for detecting, documenting, and reporting events that meet the definition of an adverse event (AE) or serious AE (SAE) and remain responsible for following up AEs that are serious, considered related to the study product or the study, or that caused the subject to discontinue the study product or study.

All AEs will be reported on the AE page of the CRF by the investigator or site staff from the completion (signature) of the ICF and until 5 days following last administration of the study product (or last procedure).

In addition to that, a SAE form should be completed. Hard copies of the ‘paper’ SAE form will be provided in the investigator study master file. Original SAE forms will be retained in the investigator study master file.

The SAE form, completed as fully as possible, must be scanned and e-mailed to the Case Management Group mailbox ([see Table 9-1](#)), with a copy to the appropriate Haleon Study Manager, with the study number and subject number in the subject line of the email **immediately and under no circumstance should this exceed 24 hours** after study site personnel learn of the event. The investigator will submit any updated SAE data to the sponsor, **immediately and under no circumstance should this exceed 24 hours** of it being available.

Table 9-1 Case Management Group mailbox

United States	PPD
---------------	-----

9.2 Definition of an AE

An AE is any untoward medical occurrence in a clinical study subject, temporally associated with the use of a study product including any washout or lead-in product (or medical device), whether or not considered related to the study product, including any washout or lead-in product (or medical device).

NOTE: An AE can therefore be any unfavorable and unintended sign (including an abnormal laboratory finding), symptom, or disease (new or exacerbated) temporally associated with the use of a study product including any washout or lead-in product (or medical device).

9.3 Definition of a SAE

A SAE is a particular category of an adverse event where the adverse outcome is serious. If an event is not an AE per definition above, then it cannot be an SAE even if serious conditions

are met (e.g. hospitalization for signs/symptoms of the disease under study, death due to progression of disease).

A serious adverse event is any untoward medical occurrence at any dose that:

- **Results in death**
- **Is life-threatening**
- **Requires inpatient hospitalization or prolongation of existing hospitalization**
- **Results in persistent or significant disability/incapacity**
- **Results in congenital anomaly/birth defect**
- **Other serious (important) medical events**

Note: Classification of an AE as ‘serious’ is based on the outcome of the event and is a factor in determining reporting requirements.

9.4 Pregnancy

Pregnancy information will be collected on all pregnancies reported while a female subject is participating in the study from the signing of informed consent until 5 days after last administration of study product.

The investigator will record pregnancy information on the appropriate form scan and e-mail it to the Case Management Group mailbox ([see Table 9-1](#)), with copy to the appropriate Study Manager, within 24 hours. Original pregnancy information forms will be retained in the investigator study master file.

The subject will be followed to determine the outcome of the pregnancy. Information on the status of the mother and infant / neonate (including concomitant medications taken by the mother during the pregnancy) will be forwarded by the investigator to the Case Management Group mailbox at Haleon ([see Table 9-1](#)), with copy to the appropriate Study Manager. Generally, follow-up will be no longer than 6 to 8 weeks following the estimated delivery date. Any termination of the pregnancy will be reported.

While pregnancy itself is not considered to be an AE, abnormal pregnancy outcomes (e.g., spontaneous abortion, fetal death, stillbirth, congenital anomalies, ectopic pregnancy) are, and should be recorded as an SAE. Any female subject who becomes pregnant while participating will be withdrawn.

9.5 Evaluating Adverse Events

9.5.1 Assessment of Intensity

The investigator or medically qualified designee will make an assessment of intensity for each AE reported during the study and will assign it to one of the following categories:

- **Mild:** An event that is easily tolerated by the subject, causing minimal discomfort and not interfering with everyday activities.
- **Moderate:** An event that is sufficiently discomforting to interfere with normal everyday activities

Property of Haleon- Confidential

May not be used, divulged, published or otherwise disclosed without the consent of Haleon

CCI

Abbreviated Clinical Protocol Template v1.0

- Severe: An event that prevents normal everyday activities.

NOTE: An AE that is assessed as severe should not be confused with an SAE. Severe is a category utilized for rating the intensity of an event; and both non-serious AEs and SAEs can be assessed as severe. For example, a headache may be severe (interferes significantly with the subject's usual function) but would not be classified as serious unless it met one of the criteria for SAEs, listed above. An event is defined as 'serious' when it meets at least 1 of the predefined outcomes as described in the definition of an SAE, NOT when it is rated as severe.

9.5.2 Assessment of Causality

The causality assessment is one of the criteria used when determining regulatory reporting requirements.

For each AE (serious and non-serious), the investigator (or medically qualified designee) **must** provide an assessment of causality on the AE eCRF page and the SAE form (subject to the classification of the AE). The investigator will also document in the medical notes that he/she has reviewed the AE and assessed causality, where applicable.

A "reasonable possibility" of a relationship conveys that there are facts, evidence, and/or arguments to suggest a causal relationship, rather than a relationship cannot be ruled out. Generally, the facts (evidence) or arguments to suggest a causal relationship should be provided.

The investigator will use clinical judgment to determine the relationship and will also consult the Safety Statement, in the determination of his/her assessment. Alternative causes, such as underlying disease(s), concomitant therapy, other risk factors, and the temporal relationship of the event to the study product will be considered and investigated.

For each AE/SAE, the investigator must document in the medical notes that he/she has reviewed the AE/SAE and has provided an assessment of causality.

The investigator's assessment of causality must be provided for all AEs (serious and nonserious); the investigator must record the causal relationship in the eCRF, as appropriate, and report such an assessment in accordance with the SAE reporting requirements if applicable.

There may be situations when an SAE has occurred, and the investigator has minimal information to include in the initial report to Haleon. **However, it is very important that the investigator always make an assessment of causality for every event prior to the initial transmission of the SAE data to Haleon.** The investigator may change his/her opinion of causality in light of follow-up information and send an SAE follow-up report with the updated causality assessment.

9.6 Follow-up of AEs and SAEs

The investigator is obligated to perform or arrange for the conduct of supplemental measurements and/or evaluations as may be indicated or as requested by Haleon to elucidate as fully as possible the nature and/or causality of the SAE or AE. This may include additional laboratory tests or investigations, histopathological examinations, or consultation with other health care professionals.

Property of Haleon- Confidential

May not be used, divulged, published or otherwise disclosed without the consent of Haleon

CCI [REDACTED] Abbreviated Clinical Protocol Template v1.0

New or updated information will be recorded on the AE eCRF page and on the SAE form (subject to the classification of the AE).

The investigator will submit any updated SAE data to Haleon within 24 hours of receipt of the information.

The investigator will submit any updated SAE data to Haleon within 24 hours.

9.7 Medical Device Incidents

The definitions and procedures detailed are in accordance with ISO 14155.

Both the investigator and the sponsor will comply with all local medical device reporting requirements.

Medical devices are being provided by Haleon for use in this study; the medical device in this study is the supplied toothbrush.

9.7.1 Definition of an Incident

A medical device incident is any malfunction or deterioration in the characteristics and/or performance of a device as well as any inadequacy in the labeling or the instructions for use which, directly or indirectly, might lead to or might have led to the death of a subject/user/other person or to a serious deterioration in his/her state of health.

Not all incidents lead to death or serious deterioration in health. The nonoccurrence of such a result might have been due to other fortunate circumstances or to the intervention of health care personnel.

9.7.2 Reporting of Incidents and Malfunctions

All incidents must be reported to Haleon **immediately and under no circumstance should this exceed 24 hours** of the investigator or designee becoming aware of the situation in order for the sponsor to fulfill the legal responsibility to notify appropriate regulatory authorities and other entities about certain safety information relating to medical devices being used in clinical studies.

The completed Incident Report Form should be scanned and emailed to the relevant Case Management Group mailbox ([see Table 9-1](#)), with copy to the appropriate Study Manager, with the study number and subject number in the subject line of the email. If there is an SAE, the completed SAE form should be sent together with this report form.

9.8 DISCONTINUATION OF STUDY PRODUCT AND SUBJECT DISCONTINUATION/WITHDRAWAL

If a subject is discontinued early from the study product (Section [9.8.1](#)) or discontinued or prematurely withdraws from the study (Section [9.8.2](#)), the reason(s) for intervention discontinuation or withdrawal and the associated date must be documented in the relevant section(s) of the CRF. If a subject is discontinued early from the study product, the subject should stay in the study and complete the remaining assessments unless they need to be withdrawn (see Section [9.8.2](#)).

Property of Haleon- Confidential

May not be used, divulged, published or otherwise disclosed without the consent of Haleon

CCI Abbreviated Clinical Protocol Template v1.0

9.8.1 Discontinuation of Study Product

A subject may be discontinued from the study product at any time whilst still in the study at the discretion of the investigator related to safety, subject consent or a potential worsening of the risk / benefit assessment from the subject of remaining on the intervention for the following reasons:

- Adverse Event
- Lack of efficacy from the intervention
- Subject request
- Subject to be withdrawn from the study (see Section [9.8.2](#))

9.8.2 Subject Discontinuation/Withdrawal

A subject may withdraw from the study at any time at his or her own request or may be withdrawn at any time at the discretion of the investigator or sponsor for safety, behavioral reasons, or the inability of the subject to comply with the protocol-required schedule of study visits or procedures.

The following circumstances require discontinuation of study product and/or premature subject withdrawal:

- Protocol violation that may impact the subject's safety
- Withdrawal of informed consent
- Subject lost to follow-up
- Unblinding of the subject
- Pregnancy

If the subject withdraws from the study and withdraws consent for disclosure of future information, no further evaluations should be performed, and no additional data should be collected. The sponsor may retain and continue to use any data collected before such withdrawal of consent.

9.8.3 Lost to Follow up

If a subject fails to return to the site for a required study visit, the investigator or designee must make every effort to regain contact with the subject (where possible, 3 telephone calls or emails or local equivalent methods) and reschedule the missed visit as soon as possible and counsel the subject on the importance of maintaining the assigned visit schedule and ascertain whether the subject wishes to and/or should continue in the study.

A subject will be considered lost to follow up and withdrawn from the study if he or she repeatedly fails to return for scheduled visits and is unable to be contacted by the study site.

If contact is made with the subject, the investigator should inquire about the reason for withdrawal, request that the subject return all products that they had been dispensed and if

appropriate request that the subject return for a final visit and follow-up with the subject regarding any unresolved adverse events (AEs).

9.9 Data Management

As used in this protocol, the term CRF is understood to refer to either a paper form or an electronic data record or both, depending on the data collection method.

The source documents which contain the source of data recorded in the CRF should be specified. The CRF and/or diary can be used as a source document at the discretion of data management.

Each subject will be assigned and identified by a unique Screening Subject Number. Any reference made to an individual subject within the study must be done using their unique Screening Subject Number.

9.9.1 Case Report Form

A CRF is a printed, optical, or electronic document designed to record the protocol required information to be reported to the sponsor on each trial subject.

For each subject who has given informed consent/assent the CRF must be completed and signed by the Principal Investigator (or authorized designee) to certify that the data are complete and correct. The investigator must maintain accurate documentation (source data) that supports the information entered in the CRF.

9.9.2 Data Handling

Documentation of all data management activities should allow step-by-step retrospective assessment of data quality and study performance.

Any changes or corrections to data will be performed in the Electronic Data Capture (EDC) System, and it will include rationale for changes. The EDC system has an audit trail, which will provide a complete record of the changes and corrections endorsed by the Investigator.

Adverse events will be coded using Medical Dictionary for Regulatory Activities (MedDRA) and any concomitant medications terms (if applicable) using an internal validated medication dictionary.

9.9.3 Data Queries

Programmed edit checks will be generated automatically, as the data are being entered into the system. Reports and listings on the CRF data will also be run, in addition to the queries already programmed and generated by the system, to raise manual queries as needed for site clarification or correction. The Clinical Dictionary Development and Management Group will raise queries as needed on safety data to code the terms (AEs and Drugs or concomitant medication) appropriately.

The study monitor will perform ongoing review the of the CRFs in accordance with the monitoring plan, to confirm that data entered into the CRF by authorized site personnel are accurate, complete, and verifiable from source documents; that the safety and rights of

Property of Haleon- Confidential

May not be used, divulged, published or otherwise disclosed without the consent of Haleon

CCI [REDACTED] Abbreviated Clinical Protocol Template v1.0

participants are being protected; and that the study is being conducted in accordance with the currently approved protocol and any other study agreements, ICH GCP, and all applicable regulatory requirements.

Any queries will be generated in the EDC System to the Investigator or designee, enabling the errors to be addressed in parallel with Data Management review. The study monitor can also run reports and listings on the CRFs, to raise manual queries as needed for site clarification or correction.

9.9.4 Processing Subject Reported Outcomes

Subject reported outcomes (NRS) will be recorded in questionnaires for later transcription into the eCRF.

Source documents recording subject-reported outcomes will be reviewed by the investigator staff and the study monitor to ensure the data, and any potential AEs or concomitant medications reported in these documents, are accurately transcribed into the eCRF.

Subjects from group toothpaste/mouthwash will complete paper copies of the Treatment Satisfaction NRS (source). To facilitate subject flow, paper forms (source) may also be used to record clinical data for later transcription into the eCRF. Transcription of NRS responses and clinical data into the eCRF must be completed within 5 days of the data being recorded. The eCRF and the subject-completed diary can be used as a source document at the discretion of Data Management.

Subject reported outcomes classed as source data will be retained by the investigator; true/certified copies may be sent to the sponsor or a third-party vendor, as required. To protect subject privacy, no PI (including subject name, initials or birth date) is to be recorded in any subject reported outcome source document that will be forwarded to the sponsor or a third party vendor.

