- 4: NBS and bleeding sites% are derived from EBI assessment
- 5: Minimum one TPI repeatability assessments during each clinical assessment day; TPI repeatability assessment at Baseline visit will be conducted after the subject's eligibility has been confirmed.
- 6: Toothpaste/mouthwash treatment arm only

Property of Haleon- Confidential

May not be used, divulged, published or otherwise disclosed without the consent of Haleon

CCI

Abbreviated Clinical Protocol Template v1.0

7: Adverse Events (AEs), Serious Adverse Events (SAEs) and medical device incidents collected immediately after subject provides consent participate in the study by the completion of the Informed Consent Form (ICF).

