5.5 Visit 4 / Week 12 (Day 84 ± 4 days)

The following procedures/ assessments will take place in the order listed below and be recorded in the CRF:

1. Collect study products returned by subjects to assess compliance. Also ask subjects about product usage compliance.
2. Review of concomitant medications and non-drug treatments/ procedures, adverse events, incidents and lifestyle restrictions
3. Subject continuance

Property of Haleon- Confidential

May not be used, divulged, published or otherwise disclosed without the consent of Haleon

CCI [REDACTED] Abbreviated Clinical Protocol Template v1.0

4. OST examination
5. OHT examination
6. MGI assessment
7. EBI assessment (including number of bleeding sites which is derived from BI assessment)
8. Plaque disclosure
9. TPI assessment
10. MGI repeatability assessment (where applicable)
11. TPI repeatability assessment (where applicable)
12. Complete optional dental prophylaxis (as if deemed necessary by examiner)
13. Record adverse events & incidents
14. Exit Satisfaction survey (toothpaste/mouthwash treatment arm only)
15. Study conclusion

Changes in concomitant medication or non-drug treatments/procedures will be documented in the CRF.

Spontaneous reporting of adverse events and those elicited by asking subjects to respond to a non-leading question such as “How do you feel?” will be assessed and any AEs recorded in the CRF.

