6.3.4 Exit Satisfaction Survey

At the end of the study (Visit 4), subjects in toothpaste/mouthwash treatment arm will be asked to rate their level of satisfaction with the toothpaste and the mouthwash using a Numeric Rating Scale (NRS).

The NRS is an 11-point ordinal scale used to assess the subject's satisfaction with the toothpaste and mouthwash. The scale ranges from 0 (completely dissatisfied) to 10 (completely satisfied), with higher scores indicative of greater satisfaction ([van Berckel et al., 2017](#)):

see example below.

Subjects will be asked to record the numeric value on the segmented scale that best describes their level of satisfaction after 12 weeks twice daily use and indicate why they select a particular score in answer to the question 'Please give more details on why you are satisfied or dissatisfied with the product' (free text response).

Example NRS - Not to Scale

In addition, subjects will be asked whether they would recommend this product to their family and friends who have gum problems. The responses will be either “yes” or “no” followed by free text describing why the choice is made.

An example of a satisfaction survey questionnaire is included in section 10.2.

Property of Haleon- Confidential

May not be used, divulged, published or otherwise disclosed without the consent of Haleon

CCI Abbreviated Clinical Protocol Template v1.0

To ensure the examiner remains blinded throughout the study, subjects will complete the exit satisfaction survey in a separate area.

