#### **4.5.1 Adverse Events and Serious Adverse Events**

All AEs will be reviewed by the Clinical Research Scientist or Designee prior to database lock and unblinding and will be coded to a system organ class (SOC) and preferred term (PT) using the Medical Dictionary for Regulatory Activities (MedDRA).

AEs will be classified as oral and non-oral on the AE page of eCRF.

Treatment emergent adverse events (TEAEs) are defined as new AEs that occur on or after the first study product use (if this date is missing, a suitable alternative will be used e.g. date of

randomization). AEs with an onset date/time prior to the first study product use at baseline visit will be considered as non-treatment emergent.

The following summary tables and listings will be presented by study product group.

- Table of TEAEs summary (Table 14.3.1.1)
- Table of TEAEs by SOC and PT (Table 14.3.1.2)
- Table of TEAEs by Oral/Non-Oral and PT (Table 14.3.1.3)
- Table of treatment related TEAEs by SOC and PT (Table 14.3.1.4)
- Table of treatment related TEAEs by Oral/Non-Oral and PT (Table 14.3.1.5)
- Listing of all AEs (Listing 16.2.7.1 for all randomized subjects; Listing 16.2.7.2 for non-randomized subjects)
- Listing of deaths (Listing 14.3.2.1)
- Listing of non-fatal SAEs (Listing 14.3.2.2)
- Listing of TEAEs leading to study or product withdrawal (Listing 14.3.2.3)
- Listing of TEAEs classified as Oral (Listing 14.3.2.4)

All incidents will be listed in Listing 16.2.7.3.

In the event that there is nothing to report, a null table or listing will be produced.

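### Only the toothpaste/mouthwash arm completes an exit survey whose adverse events go to the eCRF, which may inflate that arm's descriptive TEAE incidence

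*Protocol*

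**What the plan says.** **The survey goes to one arm.** The Week 12 visit list in Protocol 5.5 has, as step 14, "Exit Satisfaction survey (toothpaste/mouthwash treatment arm only". Footnote 6 to the Schedule of Activities (Protocol 5.1) says the same: "Toothpaste/mouthwash treatment arm only". Protocol 9.9.4 adds that "Subjects from group toothpaste/mouthwash will complete paper copies of the Treatment Satisfaction NRS (source".

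**It contains free text.** Protocol 6.3.4 gives the prompt as "Please give more details on why you are satisfied or dissatisfied with the product". The example form in Protocol 10.2 asks this once for the toothpaste and once for the mouthwash. A third box asks why the subject would or would not recommend the products.

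**AEs written in it reach the database.** Protocol 9.9.4 requires review of the source documents for subject-reported outcomes so that "any potential AEs or concomitant medications reported in these documents, are accurately transcribed into the eCRF".

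**All arms share the other routes.** Protocol 5.3 to 5.5 provide at Visits 2 to 4 for "Spontaneous reporting of adverse events and those elicited by asking subjects to respond to a non-leading question such as" an enquiry after how the subject feels. Oral soft tissue (OST) is examined at every visit and oral hard tissue at Screening and Week 12.

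**The analysis does not separate the routes.** TEAEs are the only safety endpoint (Protocol Table 2-1). SAP 4.5.1 states: "The following summary tables and listings will be presented by study product group". It then lists Tables 14.3.1.1 to 14.3.1.5, which include oral/non-oral and treatment-related breakdowns. It has no marker for the source of an event and no summary without survey-only events.

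**The concern.** AE incidence depends on how events are sought as well as on the product. Here the means of capture differ by arm, and by design. The prompt common to all arms is open and names no product. The survey asks a subject to explain dissatisfaction with a named oral product, and a minor oral complaint is a plausible answer.

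Two features could make such an event count fully against the test arm:
- Protocol 8.3.3 treats an AE with no start date as treatment emergent unless its end date precedes treatment. The example form asks for no dates.
- Protocol 9.5.2 requires a causality judgement for every AE. A survey comment names the product and, because only one arm gets the form, also reveals the arm.

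At stake is the reading of the by-product TEAE tables. A modest excess of oral or related TEAEs in the test arm could reflect tolerability, the extra route, or both. The planned tables would not show which.

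**Working it through.** **1. Is there another subject-reported instrument that would even things out?** None is scheduled. Protocol 9.9.4 mentions a subject-completed diary, but no diary appears in the Schedule of Activities or the visit lists. The survey is the only instrument of this kind.

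**2. Can an event found in the survey still be reported?** Yes. At Week 12, AEs are reviewed at step 2 and recorded at step 13, and the survey follows at step 14. Protocol 9.1 keeps AE reporting open until 5 days after the last product use or procedure. A survey-only event is therefore one that was not raised at either earlier step and was then written on the form.

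**3. Arm size.** Protocol 8.1 gives 198 randomized, about 66 per arm, for about 180 completing, about 60 per arm. Check: 180 × 1.10 = 198, and 180/(1 − 0.10) = 200. These agree to within 2 subjects. The documents give no AE rate, so there is no planned safety figure to reproduce.

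**4. Size of the effect, by assumption.** Let b be the share of subjects with a TEAE found by the common routes, equal in all arms. Let e be the share of the remaining test-arm subjects with a TEAE found only through the survey. Then:

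- apparent test-arm rate = b + (1 − b)e
- spurious excess = (1 − b)e

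With b = 10% and 66 per arm:

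| e | Apparent test-arm rate | Excess over 10% (points) | Extra subjects of 66 |
|---|---|---|---|
| 0% | 10% | 0 | 0 |
| 1% | 0.10 + 0.90 × 0.01 = 10.9% | 0.9 | 0.6 |
| 2% | 0.10 + 0.90 × 0.02 = 11.8% | 1.8 | 1.2 |
| 5% | 0.10 + 0.90 × 0.05 = 14.5% | 4.5 | 3.0 |
| 10% | 0.10 + 0.90 × 0.10 = 19.0% | 9.0 | 5.9 |

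The survey reaches only those who attend Week 12. Counted on 60 subjects, the last column from e = 1% down becomes 0.5, 1.1, 2.7 and 5.4.

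**5. Sensitivity to the base rate, at e = 5%.**
- b = 5%: 0.05 + 0.95 × 0.05 = 9.75%, a ratio of 1.95
- b = 20%: 0.20 + 0.80 × 0.05 = 24.0%, a ratio of 1.20
- b = 30%: 0.30 + 0.70 × 0.05 = 33.5%, a ratio of 1.12

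The relative distortion is greatest where the base rate is low.

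**The case against.** The strongest reply is that unequal opportunity is not the same as bias. A reader might infer that the TEAE comparison is biased as a matter of fact. The documents do not support that. If the survey yields nothing beyond what the two earlier AE steps at Week 12 picked up, there is no distortion. Subjects are also asked at Visits 3 and 4 about changes in health (Protocol 3). This stands, and it argues for a low yield.

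A reader might also infer that the protocol uses the survey to search for AEs. Protocol 9.9.4 describes review and accurate transcription, not elicitation. The prompts are directed at the products, but they ask about satisfaction as well as dissatisfaction and name no symptom. Disliking a product is not in itself an AE under Protocol 9.2. This stands too.

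It may be said that the comparison is only descriptive, with no test, interval or margin for AEs, and that any error makes the sponsor's own product look worse. Both are true, and both limit the consequence. They do not remove it, because with no inference planned readers will judge tolerability from the raw counts by arm.

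Finally, the stronger claim that the trial could not tell tolerability from ascertainment goes too far:
- OST abnormalities are summarized by visit and product in Table 14.3.4.1, from examinations made in all arms by a blinded examiner. That comparison does not depend on the survey.
- Survey comments (Listing 16.2.6.5) can be set against AEs (Listing 16.2.7.1) subject by subject.

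These help only in part. The OST examination relies on observation and palpation, so it may miss complaints that leave no sign. Matching the listings shows overlap but not which source came first.

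**Conclusion.** The point holds in a limited form. AE ascertainment is unequal by design: one arm has a route that the other two lack. Because that route can only add events, any error runs against the test arm. It may inflate that arm's descriptive TEAE incidence, mainly for oral and treatment-related events.

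The documents do not allow the size to be derived. With an assumed 10% true rate in every arm, the apparent test-arm rate runs from 10% (no survey-only yield) to 19.0% (10% yield), so the effect may be negligible or material. Both the base rate and the yields are assumptions.

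The documents do not support reading this as a demonstrated bias or as a fault in the efficacy analysis. Study success rests on overall number of bleeding sites at Week 12, which the survey does not touch. The gap worth closing is that the planned TEAE tables cannot show how many events came only from the survey.

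**What to change.** 1. **eCRF.** Add a flag to the AE page, 'first identified from exit survey', set when the event was not raised at the earlier AE steps. It would be positive in one arm only, so it reveals the arm, as does the survey page already in the eCRF. Both should be kept from blinded staff, in line with Protocol 7.3.
2. **SAP 4.5.1.** Keep every TEAE in Tables 14.3.1.1 to 14.3.1.5. Add a companion summary by product that omits survey-only events, and base between-arm statements on events found by the methods common to all arms. All events stay in Listing 16.2.7.1 and in SAE reporting.

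Survey-only events should not simply be dropped from the main tables. They meet the TEAE definition, and dropping them would remove real events from one arm only.

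An alternative is to give the toothpaste item and its comment box to all three arms. This narrows the asymmetry but does not remove it, because the mouthwash item has no counterpart in the other arms.

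The cost of the main fix is one eCRF field and a few extra summary tables, with no added subjects or visits.
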